7.3 Expedited Adverse Event Reporting

7.3.1 For MCC Investigator-Initiated Trials (IITs), study investigators and staff must report to the Overall PI any serious adverse event (SAE) that occurs after the initial dose of HCQ, during the 90-day HCQ administration (study treatment), or within 30 days of the last dose of HCQ on the SAE form.

This applies to the following categories:

- Grade 2 ocular or visual changes – any changes, regardless of attribution to the HCQ
- Grade 3 (severe) *Medical* Events – Only events that are Unexpected and Possibly, Probably or Definitely Related / Associated with the HCQ.
- ALL Grade 4 (life threatening or disabling) *Medical* Events – Unless expected AND specifically listed in protocol as not requiring reporting.
- ALL Grade 5 (fatal) Events regardless of study phase or attribution.

Note: If subject is in Long-Term Follow-Up, death is reported at continuing review.

Note: Abnormal laboratory values are not considered medical events, unless determined to be causative of SAE by the investigator or are a grade 5.

7.3.2 The following table outlines the required forms and reporting structure for clinical trials.

Study type	Expedited reporting to MCC	Expedited reporting to External Agency	Non-expedited AE	Form	IRB
IIT by MCC investigator of HCQ, a commercially available agent (non-IND and non-IDE)	Grade 2 eye/visual changes, any attribution. Grade 3 – Unexpected AE PLUS Possibly, Probably or Definitely Related ALL Grade 4 Unless expected AND listed in protocol as not requiring reporting. ALL Grade 5 events (fatal)	FDA: Suspected AE that is serious and unanticipated (not listed in IDB or in the consent)	OnCore and DSMC reporting only	Voluntary Medwatch 3500 for Serious and unanticipated OnCore for all AEs, including SAEs	Yes if it meets the IRB reporting requirements: Unanticipated Problem and/or Serious AE (use IRB AE reporting form for all correspondence with IRB)

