7.1 Expected Toxicities for Hydroxychloroquine

7.1.1 Precautions

Dermatologic Reactions to hydroxychloroquine sulfate tablets may occur and, therefore, proper care should be exercised when they were administered to any patient receiving a drug with a significant tendency to produce dermatitis.

Hydroxychloroquine Retinitis is both dose- and duration-dependent with increased risk occurring at doses exceeding 5mg/kg of actual body weight and chronic use exceeding 5 years. This trial uses an FDA-approved dose of hydroxychloroquine and is 90 days in duration. Thus, risks of hydroxychloroquine retinitis are small (less than 1%) and will be further minimized by baseline screening for retinal abnormalities, (see eligibility criteria 3.1.5 and 3.2.2), monthly assessment of adverse effects, repeat visual examinations for ocular toxicity and permanent discontinuation of hydroxychloroquine for any grade 2 or greater ocular toxicity (see 6.1, Visual Changes. The methods recommended for early diagnosis of "chloroquine retinopathy" consist of (1) fundoscopic examination of the macula for fine pigmentary disturbances or loss of the foveal reflex and (2) examination of the central visual field with a small red test object for pericentral or paracentral scotoma or determination of retinal thresholds to red. Any unexplained visual symptoms, such as light flashes or streaks, should also be regarded with suspicion as possible manifestations of retinopathy.

If serious toxic symptoms occur from **HCQ Overdosage or Sensitivity**, it is suggested that ammonium chloride (8 g daily in divided doses) be administered orally three or four days a week for several months after therapy has been stopped, as acidification of the urine increases renal excretion of the 4-aminoquinoline compounds by 20-90%. However, caution must be exercised in patients with impaired renal function and/or metabolic acidosis. See Section 8.7 for details.

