7.1.2 Adverse Reactions

The Council for International Organizations of Medical Sciences (CIOMS) frequency rating is used as follows, when applicable:

CIOMS Frequency Rating (expected % of population experiencing adverse reactions)			
Inadequate data	Not Known	0.1% - 0.9%	Uncommon
10% or greater =	Very Common	0.01 – 0.09%	Rare
1% – 9%	Common	Less than 0.01%	Very Rare

Eye Disorders

Common: Blurring of vision due to a disturbance of accommodation, which is dose dependent and reversible.

Uncommon:

- Maculopathies, which may be irreversible.
- Retinopathy with changes in pigmentation and visual field defects. In its early form, it appears reversible upon discontinuation of the drug. If allowed to develop however, there may be a risk of progression even after treatment withdrawal.
- Patients with retinal changes may be *asymptomatic initially*, or may have scotomatous vision with paracentral, pericentral ring types, temporal scotomas, abnormal color visions, reduction in visual acuity, night blindness, difficulty reading and skipping words.
- Corneal changes including edema and opacities. They are either symptomless or may cause disturbances, i.e., halos around lights especially at night, blurring of vision or photophobia. They may be transient or are reversible upon discontinuation of therapy.

Not known: Macular degeneration, which may be irreversible.

Gastrointestinal Disorders

Very common: Abdominal pain, nausea

Common: Diarrhea, vomiting

These symptoms usually resolve immediately upon reducing the dose or upon stopping treatment.

Skin and subcutaneous tissue disorders

Common: Skin rash, pruritus

Uncommon: Pigmentary changes in skin and mucous membranes, bleaching of hair, alopecia. These usually resolve readily upon cessation of therapy.

Not known: Bullous eruptions (including urticarial, morbilliform, lichenoid, maculopapular, purpuric, erythema annularecentrifugum), toxic epidermal necrolysis, erythema multiforme, Stevens-Johnson syndrome, Drug Rash with Eosinophilia and Systemic Symptoms (DRESS syndrome), photosensitivity, exfoliative dermatitis, acute generalized exanthematouspustulosis (AGEP)

AGEP has to be distinguished from psoriasis, although HYDROXYCHLOROQUINE may precipitate attacks of psoriasis. It may be associated with fever and hyperleukocytosis.

Outcome is usually favorable after discontinuation of drug.

Metabolism and nutrition disorders

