Baseline evaluations are to be conducted within 8 weeks prior to start of HCQ. Scans and ophthalmologic exam must be completed less than 8 weeks prior to the start of HCQ regimen. In the event the patient's condition is deteriorating, laboratory evaluations should be repeated more frequently, as clinically indicated and at the discretion of the treating physician. At PSA progression or symptomatic progression: PSA, history and physical/toxicity assessment, CT C/A/P and/or fluciclovine or PSMA PET scans to be performed at discretion of treating physician, per standard of care.

Study Calendar											
Procedures	Pre-study Screening	Enrollment/Baseline Visit 1, Day 0	Day 14 post-HCQ initiation	Day 30 post-HCQ initiation	Day 60 post-HCQ initiation	90 days post-HCQ initiation	6-months post-HCQ cessation	1 Year Post- HCQ cessation	2 Years Post-HCQ cessation	3 Years Post-HCQ cessation	Off-Study
HCQ Drug Dispensing		R		R	R	R					
Adverse Event Evaluation		R	R	R	R	R					
HCQ compliance (pill diary)				R	R	R					
PAR-4 blood sample ¹		R	R	R	R	R	R	R			
PBMCs blood collection ²		R		R	R						
Quality of Life ³		R				R	R	R			
Informed Consent	R										
Demographics	R										
Ophthalmologic Exam ⁴	R	← ----- S ** ----- →									
PSA (serum, one tube) ⁵	S	R		R		S	S	S			
Imaging ⁶											
Fluciclovine or PSMA PET or PET/CT scan ^{6a}	S**										
Bone scan ^{6a}	S**										
CT chest, abdomen, pelvis ^{6a}	S**										
MRI of pelvis ^{6b}	S *										
Assessment of Disease Progression ^{6c}							S * , **				
CBC w/ differential	S	*	*	S	S	S	**	**			
CMP **	S	*	*	S	S	S	**	**			
Concomitant Medications ⁷	S	S	S	S	S	S					
Medical History	S										
Height ⁸		S									
Physical Exam with vitals (including weight) and ECOG Performance status	S	**	S**	S	S	S	**	**			
Survival Status									R	R	R
Record date of ADT initiation ⁹											

Study Calendar											
Procedures	Pre-study Screening	Enrollment/Baseline Visit 1, Day 0	Day 14 post-HCQ initiation	Day 30 post-HCQ initiation	Day 60 post-HCQ initiation	90 days post-HCQ initiation	6-months post-HCQ cessation	1 Year Post- HCQ cessation	2 Years Post-HCQ cessation	3 Years Post-HCQ cessation	Off-Study

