
NOTES: * per standard of care ** at the discretion of the treating physician.
 
Legend: S = standard of care; R = research; PSA, prostate-specific antigen; PET, positron emission tomography scan; HCQ, hydroxychloroquine; PAR-4, prostate apoptosis response-4; PSMA, prostate-specific membrane antigen PET scan
 
1: Blood (1 tube) will be drawn at each of the 7 noted timepoints for PSA and PAR-4 levels; plasma is preferred (serum is acceptable). Timepoints may be +/- 72-hour window at Pre-study and Enrollment. For Day 14, Timepoints may be +/- 120-hour window. Timepoints may be +/- 28-day window at the 3-, 6- and 12-month f/u, coinciding with a clinic visit.
 
2: for collection of PBMCs (peripheral blood mononuclear cells): one tube per collection timepoint, slated for Day 0, Day 30 and Day 60. Day 0 and Day 30 timepoints have a +/- 14-day window. Day 60 has a +6 week window. This is explicated in greater detail in study lab manual.
 
3: QOL is assessed via EORTC QLQ-C30 + QLQ-PR25 at 4 timepoints 
 - at a clinic visit prior to initiation of HCQ - at a clinic visit; either the end of HCQ administration OR when HCQ is discontinued (if stop it early) - at 6-mos and 12-mos post-treatment. These final two QOL timepoints can be +/- 8 weeks, and conducted during a regularly scheduled, standard of care clinic visit. 
 
4: Requisite pre-study eye exam; Eye exam may be repeated during HCQ administration if vision complaints.
 
5: One tube of blood will be drawn at each of the 6 noted timepoints for serum PSA; this is standard of care for baseline and every 3 months (4 of the 6 draws), with two additional draws scheduled. Timepoints may be +/- 72-hour window at screening and enrollment.
 
6: Imaging at baseline, pre-study: Patients who have confirmed recurrent disease of the prostate are deemed ineligible for this trial. As such, all eligible patients will undergo standard of care imaging to identify metastases (initial evaluation of status/extent of recurrent disease), including: 6a: All eligible patients will undergo standard of care imaging to assess extent of metastatic disease at baseline; fluciclovine or PSMA PET scans are preferred; other scans (PET/CT scan, bone scan and/or CT of the chest, abdomen and pelvis) may be performed as needed at baseline to assess extent of metastatic disease, per standard of care. 6b: Additionally, eligible patients who have undergone radiation prior to study enrollment will have an MRI of pelvis (in addition to previously named imaging studies) to assess for recurrent local disease. Suspicious lesions of the prostate seen on MRI will be biopsied. 6c: Imaging on Study as work-up for disease progression: Once a patient is enrolled on-study, imaging to assess disease progression will proceed per standard of care, based on clinical indicators such as rising PSA and/or other clinical symptoms. Per RECIST 1.1, tumor re-evaluation scheduled every 6-8 weeks at the discretion of the treating physician based on clinical indicators. Notably, a rising PSA and/or other clinical symptoms could trigger a scan/imaging in an earlier timeframe.
 
7: Concomitant Medications will be assessed per standard of care at the discretion of the treating physician; during HCQ administration, Con Meds will be assessed with a particular focus on medications contraindicated for use with HCQ.
 
8: Height will be evaluated once while on-study. Height can either be assessed via the patient's medical record, and/or assessed directly (in conjunction with vital signs during a clinic visit)
 
9: ADT initiation: record date and reason for ADT initiation. Reasons for ADT initiation include: PSA/biochemical progression, Symptomatic Progression, Local Progression of baseline-detected lesions (either soft-tissue or bone lesions), or Appearance of new metastatic lesions.
											

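### AE evaluation is scheduled only to Day 90, so a man who completes dosing has no assured AE contact in the 30-day post-dose reporting window; radiation toxicity has no stated collection period

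*Combined protocol and SAP*

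**What the plan says.** **Reporting duty.** Section 7.3.1 requires SAEs to be reported from the first dose, "during the 90-day HCQ administration (study treatment), or within 30 days of the last dose of HCQ on the SAE form". Its list of reportable categories includes Grade 2 ocular or visual changes: "any changes, regardless of attribution to the HCQ".

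**Schedule.** In the Study Calendar (Section 10), the row "Adverse Event Evaluation" is marked at Day 0, 14, 30, 60 and 90. It is blank at 6 months, at 1, 2 and 3 years after HCQ, and at off-study. Section 5.3 sets dosing at 90 days.

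**Other provisions.**
- Section 7.1.1 lists "monthly assessment of adverse effects" among the safeguards against retinal toxicity.
- Calendar note 4 says: "Eye exam may be repeated during HCQ administration if vision complaints".
- The text above the calendar provides an event-driven check: "At PSA progression or symptomatic progression: PSA, history and physical/toxicity assessment", with imaging at the treating physician's discretion.
- Section 5.6 follows an AE to its outcome only in men taken off study because of it.

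**Radiation toxicity.** Section 1.2 makes it part of a secondary objective, graded by CTCAE v5.0. The only period given there, the time on HCQ, attaches to HCQ toxicity. Section 11.2.1 gives a starting point for HCQ toxicity only, and 13.3.2 gives no period.

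**The concern.** A reporting window that outlasts the last planned contact depends on events reaching staff by some other route. Grade 4 and 5 events often will. A Grade 2 visual change, or an event treated at another hospital, is less certain to, and the visual change is a category the protocol chose to make reportable whatever its cause. The monthly rhythm relied on in 7.1.1 stops one month before the reporting window closes.

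For radiation toxicity the problem is interpretation. With no stated period, a reader of the incidence table cannot tell what time at risk it describes.

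Only the completeness and clarity of descriptive safety tables are at stake. Section 13.3.2 plans frequency and incidence tables, the plan states no stopping rule that uses them, and the PAR-4 endpoint is not touched.

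**Working it through.** The plan gives no figure of its own on this point, so the check is calendar arithmetic.

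**Inputs.** Last dose Day 90 (5.3); reporting window 30 days (7.3.1); AE evaluations at Day 0, 14, 30, 60 and 90 (Section 10); local treatment about Day 14, because HCQ starts two weeks before it (5.3); 20 men (13.1.2).

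1. *Window.* It closes at 90 + 30 = Day 120. AE evaluations after Day 90 and up to Day 120: none. If the first dose is counted as Day 0, the 90th falls on Day 89 and the Day 90 visit covers 1 of the 30 days.

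2. *Next calendar column.* Six months after HCQ is about 90 + 182 = Day 272, which is 272 − 120 = 152 days after the window closes. The widest window stated for that column is the QOL one: "These final two QOL timepoints can be +/- 8 weeks, and conducted during a regularly scheduled, standard of care clinic visit". Its early edge is 272 − 56 = Day 216, still 216 − 120 = 96 days after. The AE row is blank there in any case.

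3. *Standard-of-care PSA rhythm.* Note 5 describes draws every 3 months: about 90 + 90 = Day 180, or 60 days after the window closes.

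4. *Moving the Day 90 visit.* Note 1 allows the 3-month PAR-4 timepoint ±28 days. At the late edge (90 + 28 = Day 118) an AE check made at that visit would cover 28 of the 30 days. At the early edge (90 − 28 = Day 62) it would leave 120 − 62 = 58 days without one.

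5. *Early stoppers.* With a last dose on Day 60, 72, 80 or 89, the Day 90 evaluation falls inside the 30 days, provided the visit is still held. The gap therefore concerns men who complete dosing.

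6. *Likely number of events.* Section 7.1.1 puts retinitis risk in this trial below 1%: 20 × 0.01 = 0.2, so fewer than 0.2 expected cases over the whole trial. The frequency bands in 7.1.2 give, for retinopathy (0.1% to 0.9%), 20 × 0.001 = 0.02 to 20 × 0.009 = 0.18 cases. For dose-dependent, reversible blurring (1% to 9%) they give 20 × 0.01 = 0.2 to 20 × 0.09 = 1.8. None of these rates is specific to the 30 days after the last dose, so the number missed cannot be computed; it can only be a part of these totals.

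7. *Radiation toxicity.* Scheduled evaluation covers 90 − 14 = 76 days from the start of local treatment.

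**The case against.** The best defence is that nothing here contradicts anything else. Section 7.3.1 imposes a duty to report and promises no visit; for fatal events the clock in 7.3.3 runs from when staff learn of the event. That is right, and it confines the point to active ascertainment.

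There are also other routes by which staff may learn of an event. Note 1 lets the 3-month timepoint run late. Note 6c mentions tumor re-evaluation every 6 to 8 weeks at the physician's discretion; counted 8-weekly from Day 0, one falls on Day 112. Section 11.4.1 assesses survival status at continuing clinic visits through the first year. Appendix C tells men to contact their doctor promptly about eye problems and gives after-hours contacts. All of this stands, and a reader who inferred that there will be no contact at all between Day 90 and Day 120 would go too far. But none of these contacts is required to fall in the window, and the Appendix C sheet does not say how long after the last dose it applies.

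A reader might also take the statement in 7.1.2 that "there may be a risk of progression even after treatment withdrawal" as evidence of substantial eye risk after dosing. The documents do not support that. The same entry says the early form appears reversible on stopping and makes later progression conditional on the change having been allowed to develop. Section 7.1.1 links higher risk to larger doses by weight and to use beyond 5 years.

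Two further inferences fail. HCQ toxicity as defined in 1.2 is confined to the dosing period, which the calendar covers. And the radiation objective does not mention late toxicity; the AE row can fairly be read as implying collection to Day 90. What remains is that this period is nowhere stated.

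Finally, a Day 120 contact may exist in the DSMC procedure (7.3.3) or the Data Management Plan (13.4), neither of which is in these documents.

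**Conclusion.** The point holds in a limited form. For a man whose last dose is on Day 90, the protocol schedules and assures no AE contact in the 30 days during which events remain reportable. Separately, the radiation-toxicity part of a secondary objective has no stated collection period, and scheduled evaluation ends about 76 days after local treatment begins.

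Severity is minor. The expected number of missed events is small and cannot be pinned down from the rates given. The effect is limited to descriptive safety tables. The conclusion assumes nominal visit days and that no unseen document already provides a 30-day contact.

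**What to change.** 1. In the calendar's AE row, add one telephone AE/SAE check 30 days after the last HCQ dose for every man, with a direct question on vision. Sections 5.3 and 11.1 already provide for staff calls. If the Data Management Plan or DSMC procedure already contains such a contact, show it in the calendar.
2. In 11.2.1, state the period the radiation-toxicity table covers: start of local treatment to the last scheduled AE evaluation. With the call in place, that is about 120 − 14 = 106 days for a man completing on Day 90.

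Optionally, mark CTCAE radiation toxicity at the existing 6-month and 1-year visits (at most 20 × 2 = 40 visits) and end the stated period at 1 year. This is a choice of scope; the objective as written does not require it.

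The cost is about 20 calls, a calendar entry and one sentence. The downside is a little staff time and a possibly slightly higher reported event count. The definition of HCQ toxicity in 1.2 can stay as it is.

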7.2 Adverse Event Characteristics

7.2.1 CTCAE v.5.0: For AE reporting, descriptions and grading scales of the NCI Common Terminology Criteria for Adverse Events CTCAE version 5.0 will be utilized. All appropriate treatment areas have access to a copy of the CTCAE version 5.0.

Additionally, a copy of the CTCAE version 5.0 can be downloaded from the CTEP web site
http://ctep.cancer.gov/protocolDevelopment/electronic_applications/ctc.htm.

7.2.2 For expedited reporting purposes only:

AEs for HCQ noted in Section 7.1 should be reported only if the adverse event varies in nature, intensity or frequency from the expected toxicity information which is provided.

Other AEs that do not require expedited reporting are outlined in Expedited Adverse Event Reporting (Section 7.3).

7.2.3 Attribution of the Adverse Event (AE):

Definite – The AE is *clearly related* to the HCQ.
Probable – The AE is *likely related* to the HCQ.
Possible – The AE *may be related* to the HCQ.
Unlikely – The AE is *doubtfully related* to the HCQ.
Unrelated – The AE is *clearly NOT related* to the HCQ.

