7.3.3 MCC Expedited Reporting Guidelines for MCC IITs

Investigators within MCC will report SAEs directly to the MCC DSMC per the MCC DSMC SOP and the University of Kentucky IRB reporting policy.

Attribution	MCC Reportable AEs				
	Gr. 2 AE Expected	Gr. 3 AE Unexpected	Gr. 4 AE Expected	Gr. 4 AE Unexpected	Gr. 5 AE Expected or Unexpected
Unrelated Unlikely	Only for eye/visual changes	Not required	5 calendar days [#]	5 calendar days	24 hours*
Possible Probable Definite	Only for eye/visual changes	5 calendar days	5 calendar days [#]	5 calendar days	24 hours*

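### The expedited-reporting trigger for eye events omits 'or greater', so an expected or unrelated Grade 3 eye event is not on the Section 7.3 clock

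*Combined protocol and SAP*

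**What the plan says.** Section 7.3.1 lists what investigators and staff must report to the overall PI, from the first dose of HCQ to 30 days after the last. The first category is "Grade 2 ocular or visual changes – any changes, regardless of attribution to the HCQ". For Grade 3 medical events the condition is "Only events that are Unexpected and Possibly, Probably or Definitely Related / Associated with the HCQ", with no exception for the eye. Grade 4 events are all reportable unless they are expected and specifically named as exempt. Grade 5 events are all reportable.

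Table 7.3.2 repeats both rules: "Grade 2 eye/visual changes, any attribution" and "Grade 3 – Unexpected AE PLUS Possibly, Probably or Definitely Related".

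Table 7.3.3 sets the timing for reports to the DSMC. Its only Grade 2 column is headed as expected events, and both attribution rows read "Only for eye/visual changes", with no time limit. Its only Grade 3 column is for unexpected events: no report if unrelated or unlikely, 5 calendar days if possible or stronger. Grade 4 has 5 calendar days and Grade 5 has 24 hours.

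Section 7.2.2 says that, for expedited purposes, HCQ events listed in Section 7.1 "should be reported only if the adverse event varies in nature, intensity or frequency from the expected toxicity information which is provided". Section 7.1.2 lists blurred vision, maculopathies, retinopathy with field defects, corneal changes and macular degeneration.

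Elsewhere the protocol sets its eye threshold differently. Section 7.1.1 refers to "permanent discontinuation of hydroxychloroquine for any grade 2 or greater ocular toxicity", and the Visual Changes table in Section 6.1 uses the same cut-off.

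**The concern.** An eye-specific trigger that ignores attribution exists to override the general filters on expectedness and relatedness. As worded, it does so at Grade 2 and the filters return at Grade 3. A site following the text must expedite Grade 2 blurring that it considers unrelated. It need not expedite a definitely related Grade 3 retinopathy, because that is expected, nor a Grade 3 visual loss judged unrelated.

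Attribution may be hard to judge in this population. Section 3.2.2 admits, at the treating physician's discretion, men with cataracts, severe retinopathy, severe visual impairment or one functional eye, and a visual loss in such a man could be put down to the earlier condition. Note 4 of the study calendar makes repeat eye examinations optional and prompted by complaints, so event reports are one of the main ways a problem would surface. At stake is how promptly a Grade 3 eye event reaches the overall PI and the DSMC. Whether it is recorded at all is not in question.

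**Working it through.** No sample-size or power figure is involved. The check is a cross-tabulation of the reporting rules for an eye event, by grade, expectedness and attribution (unrelated or unlikely, against possible or stronger). Each grade has 2 × 2 = 4 combinations.

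**Step 1. Sections 7.3.1 and 7.3.2 taken alone.**

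| Grade | Expected, unrelated | Expected, related | Unexpected, unrelated | Unexpected, related | Expedited |
|---|---|---|---|---|---|
| 2 (eye trigger) | yes | yes | yes | yes | 4 of 4 |
| 3 (general rule) | no | no | no | yes | 1 of 4 |
| 4 (general rule) | yes | yes | yes | yes | 4 of 4 |
| 5 (general rule) | yes | yes | yes | yes | 4 of 4 |

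The Grade 4 row would fall to 2 of 4 for an expected event named as exempt, but the protocol names no eye event in that way.

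**Step 2. Table 7.3.3.** At Grade 3 it gives the same 1 of 4: unexpected and unrelated is marked as not required, and expected Grade 3 has no column. At Grade 2 it covers only the two expected combinations, 2 of 4, because an unexpected Grade 2 eye event has no cell. So 7.3.3 is narrower than 7.3.1 at Grade 2. The Grade 3 gap does not depend on this table, because 7.3.1 states the rule in text.

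**Step 3. Section 7.2.2.** Read literally, it makes the two expected Grade 2 combinations conditional on the event departing from the listed information. The eye trigger in 7.3.1 has no such condition, so the two sections cannot both be followed for a listed Grade 2 eye event.

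Could 7.2.2 bring a listed Grade 3 event back in, as differing in intensity? Section 7.1.2 gives frequency bands and descriptions but no CTCAE grade for eye events, so there is no reference intensity. Such a reading also would not remove the two Grade 3 conditions in 7.3.1, and it would not help with an event judged unrelated.

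**Step 4. Expected numbers.** Section 7.1.1 puts the risk of HCQ retinitis in this trial below 1%. Section 13.1.2 plans 20 patients. The expected count is below 0.01 × 20 = 0.2 events of any grade. Section 7.1.2 rates blurred vision as common (1% to 9%), giving 0.2 to 1.8 events, and retinopathy, maculopathy and corneal changes each as uncommon (0.1% to 0.9%), giving 0.02 to 0.18 events each. These figures cover all grades, so Grade 3 would be fewer. They are drug-reaction rates and do not include unrelated eye disease, for which the protocol gives no figure.

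**The case against.** A reader might infer that the protocol reports eye toxicity in reverse order of severity, or that its serious end reaches the overall PI and the DSMC only through routine data. The documents support neither reading.

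- Grades 4 and 5 are expedited under the general rules at any attribution. The dip is at Grade 3 only.
- Section 4.4 makes the PI or designee responsible for notifying the DSMC and IRB of significant events that are serious, unexpected or both. A serious but expected Grade 3 retinal event can qualify, whatever its attribution. The same section has the DSMC review all adverse events, and the IRB column of table 7.3.2 includes serious events.
- The note at the end of Section 6.2 asks for other Grade 3 or 4 toxicities to be discussed with the study PIs. The 6.1 tables cover only events deemed at least possibly related, so a Grade 3 eye event judged unrelated can fall under that note.
- Section 7.5 puts every event into routine reporting, and related events at Grade 2 or above already have a management rule in 6.1. Expected numbers are small, and screening and accrual run through one centre's clinics.

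All of this stands, and it limits the point. It does not close the gap. Section 4.4 defers to SOPs that are not part of these documents. The 6.2 note has no deadline, and routine reporting is by definition not expedited. None of these routes gives the affected Grade 3 events the 7.3 timeline.

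The 4 of 4 at Grade 2 rests on 7.3.1 and 7.3.2 alone. Under 7.3.3 it is 2 of 4, and 7.2.2 would narrow it differently. That disagreement is itself part of the finding.

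**Conclusion.** The expedited-reporting rules are wrong as written, within a narrow scope. On the text of 7.3.1 and 7.3.2, three of the four kinds of Grade 3 eye event are outside expedited reporting, while all four kinds at Grade 2 are inside it. The listed retinal and corneal events, being expected, are among those left out at Grade 3 even when definitely related. Separately, 7.2.2, 7.3.1, 7.3.2 and 7.3.3 do not agree on Grade 2 eye events, and 7.3.3 gives those events no deadline.

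This rests on two readings: that an event listed in Section 7.1 counts as expected, and that the eye trigger means Grade 2 and no higher. An omitted phrase is the likeliest explanation, since 6.1 and 7.1.1 use the wider threshold for the same toxicity and no reason is given for a narrower one in reporting. The combination counts describe coverage of the rules and are not a measure of risk.

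A reader might go further and conclude that a retinal signal would be recognised late, or that the protocol ranks eye toxicity as its leading risk. The first is speculative, given the small expected numbers and the other routes. The second is an inference from the screening exam and the dedicated rules, because the protocol does not rank its risks.

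**What to change.** Amend the reporting text in four places:

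1. **7.3.1:** reword the eye category as *Grade 2 or greater ocular or visual changes, expected or unexpected, any attribution*. This matches the threshold wording in 6.1 and 7.1.1.
2. **Table 7.3.2:** make the same change.
3. **Table 7.3.3:** replace the Grade 2 column with an eye/visual column of the same scope, and give it the table's existing 5-calendar-day limit. Leave Grade 5 as it is.
4. **7.2.2:** add *except eye/visual changes, which follow 7.3.1*.

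If a Grade 2-only trigger was intended, the protocol should say so and explain why the Grade 3 conditions then apply.

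The change affects reporting wording only. It leaves dosing, eligibility, the primary endpoint and the discontinuation rule untouched. The cost is at most a few additional expedited reports among 20 patients.
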